- Incidence of medications with possible antiviral activity (hydroxychloroquine, lopinavir/ritonavir, ribavirin or remdesivir) or adjunctive therapy use (e.g., tocilizumab)
- Incidence (and length in days) of extracorporeal membrane oxygenation use
- Incidence (and length in days) of renal replacement therapy use
- Intolerance of high dose (50mg) losartan after tolerating 25mg
- Change in SARS-CoV-2 viral load determined by quantitative PCR

Inclusion criteria:

1. Age ≥ 18 years admitted to the University of Kansas Health System.
2. Confirmation of infection with SARS-CoV-2 by PCR testing.
3. Hypoxic respiratory failure
 - Requiring mechanical ventilation or oxygen OR a SpO₂ $\leq 94\%$ on room air or a P_aO₂/F_iO₂ (P/F) ratio <300 OR tachypnea (respiratory rate ≥ 24 breaths/min).
4. Other concomitant medications such as antivirals and hydroxychloroquine are allowed.
5. Participants prescribed standard of care (SOC) losartan (25mg QD) within 48 hours of consenting may be considered for enrollment if eligibility criteria are met based on EMR data assessment, i.e. no other ARB or ACE prior to SOC medication administration. If participant is eligible and signs consent form, investigational losartan 25mg QD will be ordered to replace SOC prescription on the following scheduled dose.

Exclusion criteria:

1. Pregnancy.
2. Respiratory failure due to a process other than COVID-19.
3. Intolerance to ARBs.
4. Previous treatment with an ARB or ACE inhibitor (see exception in inclusion criteria).
5. Current chronic use of medication with known interactions with losartan including NSAIDs (intermittent prior use is acceptable), potassium supplementation aliskiren.
6. Blood pressure less than 90 mm Hg systolic or 60 mm Hg diastolic recorded on at least two readings 30 min apart.
7. Need for vasopressors, unless norepinephrine ≤ 0.1 μ g/kg/min
8. Hyperkalemia (serum K⁺ > 5.5 mM).
9. Known cardiac failure (left ventricular ejection fraction $\leq 35\%$), renal insufficiency (Cockcroft-Gault < 30 mL/min/1.73 m² or urinary output < 20 mL/h), hepatic failure (LFTs > 5 x normal upper limit).
10. Known renal artery stenosis.
11. Neurological, psychiatric, endocrine or neoplastic diseases that are judged to interfere with participation in the study.
12. On another interventional trial (including one for COVID-19) that excludes participation.
13. Meeting all inclusion criteria for more than 48 hours prior to Day 0

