- Monitor subject for safety and losartan stoppage criteria.
- For participants following inclusion criteria #5: Day 0 assessments should be performed on enrollment day as well as day 1 **or** day 2 based on first dose of SOC losartan administration.

Day 3:

- Dose escalation: On study day 3 if none of the parameters listed below are met the dose of losartan will be increased to 50 mg once daily.

Day 4 until study completion:

- Monitor subject for safety and losartan stoppage criteria.
- Treatment group will have nasopharyngeal swab and research plasma collected at end of study.

Stoppage criteria for losartan

- Hyperkalemia (persistent values >5.5 mM recorded on at least 2 readings).
- Worsening renal function (Cockcroft-Gault <30 mL/min/1.73 m²) or urinary output <20 mL/h.
- Skin rashes, palpitations or other moderate or severe adverse events (interference with usual daily activities) without clear explanation should warrant immediate cessation of treatment and notification of study personnel.
- Development of sustained hypotension defined as SBP <90 mmHg, DBP <60 mmHg recorded on at least two readings 30 min apart or use of norepinephrine >0.1 µg/kg/min.

[figure not shown]
- Any change in monitor lab parameters deemed significant and potentially related to study drug by the Investigator.

Dose de-escalation criteria

- Any change in monitoring parameter after dose increase from 25 mg to 50 mg that is considered significant by the investigator will trigger a decrease dose back to 25 mg
- If abnormal parameter is resolved and, in the opinion of the investigator, is unlikely to be related to losartan will increase dose back to 50 mg
- If de-escalation criteria is met after re challenging 50mg dose, the dose will be once more decreased to 25mg until the end of the study.

Criteria for resuming after stopping

- If stoppage criteria have resolved and reason for stoppage is felt to be unlikely or possibly related to losartan, discussion of resumption of losartan with medical monitor
- Dose resumption will start at 25 mg. If stopped at 25 mg → the dose will be continued for three days followed by increase to 50 mg if tolerated. If stopped at 50 mg, 25 mg will be started and escalated to 50 mg the day after if tolerated.

Control

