Patients that request to not be treated with Losartan will be approached by the study team to request permission for their standard of care treatment and data be followed and recorded by the research team for this study. Patients that agree, will sign the consent form, but will not provide a blood sample for research. We will also collect medical information relating to safety criteria on historical controls treated at the University of Kansas Hospital in the 30 days prior to the study start date (3/25/2020) and during the study period. These controls will be retrospectively identified through query of the electronic health record. We will attempt to include controls that meet all criteria for enrollment into the study but to achieve a ratio of controls to study participants of 2:1 may need include some with exclusion criteria (excluding prior ACE inhibitor or ARB use). Controls identified retrospectively will not undergo informed consent as this represents minimal risk.

Losartan

Losartan is an FDA-approved ARB widely prescribed for treatment of hypertension, heart failure, and for renal protection in patients with diabetes. The doses proposed in this study are well tolerated by non-hypertensive patients without significant effect on blood pressure. The proposed starting dose of losartan is 25 mg orally per day with increase to 50 mg orally per day on day 3 if tolerated until they patient is discharged from the hospital, met stoppage criteria (above) or completed 14 days of therapy.

The most common side effects are fatigue and dizziness. Serious adverse events that are rare include angioedema, hypotension, renal dysfunction or failure, blood dyscrasias, hepatitis, or rhabdomyolysis. The following are meant to mitigate risk to the subjects: Dosing will be done in an inpatient setting with clinically indicated close observations of blood pressure and organ dysfunction (blood work). Subjects with hyperkalemia, renal dysfunction, or who are taking potassium supplements will not be enrolled into the study. Participants will be given written descriptions of potential side effects and potential responses to the side effects.

Sample size and Statistics

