Since there is no information on the effects of losartan in human beings suffering from COVID-19, a statistical analysis based on efficacy is not possible. From a safety perspective, we would accept considering losartan equivalent or superior to the comparison group not receiving losartan (historical or no consent) if there is a $\pm 20\%$ difference in total AE/SAEs. Historical controls will be matched with study participants based on upon age, sex and disease severity in a 2:1 ratio for safety comparison. From a safety perspective, losartan's long track record as a safe medication is reassuring. See section on DSMB for further details on safety monitoring and analysis.

Confidentiality

All information provided by the subject to the investigators, and all information that is collected about the subjects by the investigators, shall be kept confidential to the extent that is provided by law. Computer data files will be stored and backup up to secure, HIPPA compliant, password protected computers and servers. Electronic data capture into REDCap system will be used. Access to these databases will be restricted to individuals associated with the study who require access to the data to perform their duties. These individuals will be named by the principal investigator prior to initiation of the clinical trial. The subject's actual identity cannot be ascertained exclusively from these data and the subject's name shall not be used in any publications. All investigators and staff involved in the research protocol will be bound by this agreement of confidentiality.

Adverse Event and Serious Adverse Event Documentation

Definition of an Adverse Event

For the purpose of this protocol, an AE will be defined as any untoward medical occurrence in a subject during the study listed under DMSB - Anticipated Adverse Events and Grading Scale section of this protocol as well as safety monitoring data listed on table 1 as well as stoppage criteria for losartan.

The event does not necessarily have a causal relationship with the treatment. AEs will be collected for both study groups, treatment and control from the time the ICF is signed until the subject completes study participation.

Definition of a Serious Adverse Event

An SAE is any AE that meets any of the following outcomes:

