Hemoglobin	Hemoglobin (Hgb) <LLN - 10.0 g/dL; <LLN - 6.2 mmol/L; <LLN - 100 g/L Follow up	Hgb <10.0 - 8.0 g/dL; <6.2 - 4.9 mmol/L; <100 - 80g/L ; follow up	Hgb <8.0 - 6.5 g/dL; <4.9 - 4.0 mmol/L; <80 - 65 g/L; transfusion indicated; stop losartan, follow up	Life-threatening consequences; urgent intervention indicated; stop losartan	Death
Leukocytes	<LLN - 3000/mm3; <LLN - 3.0 x 10e9 /L; follow closely	<3000 - 2000/mm3; <3.0 - 2.0 x 10e9 /L; stop losartan; follow up	<2000 - 1000/mm3; <2.0 - 1.0 x 10e9 /L; stop losartan; follow up and further investigation	<1000/mm3; <1.0 x 10e9 /L; stop losartan; follow up and further investigation	
Platelets	<LLN - 75,000/mm3; <LLN - 75.0 x 10e9 /L; follow closely	<75,000 - 50,000/mm3; <75.0 - 50.0 x 10e9 /L; follow closely, stop losartan	<50,000 - 25,000/mm3; <50.0 - 25.0 x 10e9 /L; follow closely, stop losartan,	<25,000/mm3; <25.0 x 10e9 /L; follow closely, stop losartan, transfer to ICU	
Angioedema	N/A	N/A	Angioedema occurs – mild: stop losartan, transfer to ICU	Angioedema occurs – severe tongue swelling: stop losartan, transfer to ICU	Death
Hypotension (for participants in ICU on sedation for mechanical ventilation ONLY)	Initiation of vasopressors	Increase in vasopressor dose to >0.1; stop losartan, follow up	Persistent hypotension without alternative cause; stop losartan, follow up	Irreversible end organ damage related to hypotension; stop losartan, follow up	Death
Hypotension (for participants NOT in ICU on sedation for mechanical ventilation)	Asymptomatic, intervention not indicated	Non-urgent medical intervention indicated; stop losartan, follow up	Urgent medical intervention or transfer to ICU indicated; stop losartan, follow up	Life-threatening and urgent intervention indicated; losartan, follow up	Death

Creatinine	>1 - 1.5 x baseline; >ULN - 1.5 x ULN; follow up	>1.5 - 3.0 x baseline; >1.5 - 3.0 x ULN; close follow up	>3.0 baseline; >3.0 - 6.0 x ULN; stop losartan, nephrology intervention	>6.0 x ULN; stop losartan, nephrology intervention	
Potassium&	>ULN to 5.5 mmol/L; monitor	>5.5 - 6.0 mmol/L; stop losartan, close follow up	>6.0 - 7.0 mmol/L; urgent intervention indicated, stop losartan, intervention	>7.0 mmol/L; life-threatening consequences; stop losartan, intervention	

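### Uncapped use of ineligible retrospective controls to reach 2:1 can raise the control adverse-event total and so ease the ±20% safety criterion

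*Combined protocol and SAP*

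**What the plan says.** **Control section.** Retrospective controls come from the health record. Eligible patients are tried first: "We will attempt to include controls that meet all criteria for enrollment into the study". The relaxation follows: "to achieve a ratio of controls to study participants of 2:1 may need include some with exclusion criteria (excluding prior ACE inhibitor or ARB use". No number, order of relaxation, reporting duty or sensitivity analysis is attached to it. These controls give no informed consent. A second control group, patients who decline losartan but agree to data collection, does sign a consent form.

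**Sample size and Statistics.** Losartan is judged against the comparison group by a ±20% "difference in total AE/SAEs". The scale (relative or absolute) and the unit (events or patients) are not stated. Historical controls are matched 2:1 on age, sex and disease severity; no severity measure is named.

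**Definition of an Adverse Event.** Adverse events include the Table 1 findings and the losartan stoppage criteria. Collection starts when the consent form is signed.

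**Losartan section.** The treated group is selected the other way: "Subjects with hyperkalemia, renal dysfunction, or who are taking potassium supplements will not be enrolled into the study".

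**The concern.** Safety is the primary hypothesis, and the ±20% rule is the only numerical between-group safety criterion. Several conditions that bar a patient from losartan are also adverse events under this protocol. A control admitted with one of them may already meet an event threshold, or be close to it, when observation starts. The control total could then be higher because of who was selected, and losartan would compare better for a reason unrelated to the drug. The clause leaves both its use and its extent open, and the controls' outcomes may already be in the chart when they are chosen.

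A related gap affects every retrospective control, eligible or not. Without a consent form they have no written start date for event collection, and no general rule removes abnormalities already present at baseline. Deleting the relaxation would not close this gap, but the gap makes the relaxation more harmful.

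**Working it through.** **Step 1. Compare the exclusions with the adverse-event definitions.**

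| Exclusion | Limit | Matching adverse-event definition |
|---|---|---|
| 6 | BP below 90 systolic or 60 diastolic, two readings 30 min apart | Stoppage criterion with the same limits, worded as a new development |
| 7 | Vasopressors, except norepinephrine up to 0.1 | Stoppage criterion: norepinephrine above 0.1. Table 1, sedated-ICU row, Grade 2: dose raised above 0.1 |
| 8 | Potassium above 5.5 | Table 1 Grade 2 or higher. The stoppage criterion needs two readings: "Hyperkalemia (persistent values >5.5 mM recorded on at least 2 readings" |
| 9, renal | Cockcroft-Gault below 30 or urine below 20 mL/h | Stoppage criterion with the same limits |
| 9, hepatic | LFTs above 5 x upper limit | Table 1 Grade 3 or higher |
| 5 | "Current chronic use of medication with known interactions with losartan including NSAIDs (intermittent prior use is acceptable), potassium supplementation aliskiren" | None directly; potassium supplementation bears on the potassium event |
| 9, LVEF; 1, 3, 10-13 | Various | No overlap shown |

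The creatinine grade is partly relative to baseline (Grade 1: ">1 - 1.5 x baseline; >ULN - 1.5 x ULN; follow up"). The potassium and liver-enzyme grades have no such part. The entry screen does not make losartan patients free of all Table 1 findings: they may enter with lower grades, for example liver enzymes up to 5 x the upper limit.

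**Step 2. Inputs.** From the protocol: 50 losartan patients; at 2:1, 2 x 50 = 100 controls; margin ±20%. It gives no expected event rate, ineligible share, error rate or power, so it has no figure to reproduce here. Everything else below is assumed, including acceptance on the point estimate.

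**Step 3. Shift in the event total.** Let L be events per eligible control, k the extra events per ineligible control, and f the ineligible share.

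Control mean = (1 − f)L + f(L + k) = L + fk, so the relative rise is fk/L.

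With k = 1:
- f = 5%: 0.05/1 = 5% at L = 1; 0.05/2 = 2.5% at L = 2; 0.05/4 = 1.25% at L = 4.
- f = 20%: 20%, 10% and 5%.

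A true losartan rate ratio of 1.5 then appears, at f = 20%, as 1.5/1.20 = 1.25 (L = 1) or 1.5/1.05 = 1.43 (L = 4).

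**Step 4. Chance of acceptance.** This is P(losartan mean ≤ 1.2 x control mean), computed exactly, with true rate ratio 1.5 and k = 1. Counts per patient are negative binomial with variance = mean + 0.5 x mean².

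| L | f = 0 | f = 5% | f = 20% |
|---|---|---|---|
| 1 | 13.6% | 19.4% | 42.4% |
| 2 | 9.2% | 11.9% | 22.3% |
| 4 | 6.6% | 7.7% | 11.9% |

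With Poisson counts, going from f = 0 to f = 20%: 7.7% to 39.7% (L = 1), 2.2% to 11.8% (L = 2), 0.2% to 1.2% (L = 4).

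**Step 5. Patients instead of events.** Let p and q be the proportions with an event among eligible and ineligible controls. The control proportion is p + f(q − p). Take q = 70%.
- Absolute 20-point margin, true excess 30 points, f = 20%. At p = 30% the control proportion is 30 + 0.2 x 40 = 38%, and acceptance goes from 12.7% to 42.6%. At p = 50% it is 50 + 0.2 x 20 = 54%, and acceptance goes from 10.6% to 23.0%.
- Relative 20% margin, true risk ratio 1.5. At p = 50%, acceptance goes from 4.4% to 5.8% (f = 5%) or 12.1% (f = 20%). At p = 30% it goes from 16.3% to 53.6% (f = 20%). Because Table 1 counts Grade 1 findings, p may be well above 30%, so this last case is the less representative one.

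**Step 6. Precision lost with m controls instead of 100.** Factor = √(1/50 + 1/m) / √(1/50 + 1/100). For m = 80, 70, 50, 40 and 30 this is 1.041, 1.069, 1.155, 1.225 and 1.333.

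**The case against.** The case for the plan has real substance.

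- **The clause may be little used.** Eligible controls come first and the text speaks only of some exceptions. At a 5% share the effect is modest, as Step 4 shows. This stands, but nothing in the text holds the share there.
- **Not every ineligible control brings extra events.** A pregnant patient, or one who met the inclusion criteria for more than 48 hours, may bring none. If the clause mainly admits such patients, the average k could be near zero. This stands.
- **Matching and onset wording help.** Matching on severity could absorb part of the shift. Events must arise during the study, and the hypotension and renal stoppage criteria are worded as new or worsening. The Table 1 footnote also recommends repeating a high potassium value. These limit the problem only in part: no severity score is named, retrospective controls have no start date, and the potassium and liver-enzyme grades ignore baseline.
- **Consenting decliners have a start date and may dilute the effect.** This holds if they are pooled with the retrospective controls, which the protocol does not settle.

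A reader might also infer more than the documents support:

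- *That all of exclusions 5-9 are adverse events.* Exclusion 5 is medication use, an indirect risk factor, and the LVEF limit in 9 is not a listed event.
- *That waiving exclusion 2 ("Respiratory failure due to a process other than COVID-19") admits patients without COVID-19.* The clause relaxes exclusions only. PCR confirmation and hypoxic respiratory failure remain inclusion criteria, although the cause of the failure could differ.
- *That the comparison as a whole is biased in favour of losartan.* Symptoms such as fatigue and dizziness may be under-recorded in retrospective charts, which would act the other way. The net direction is unknown.

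**Conclusion.** The concern holds in conditional form. If the clause is used for patients who meet exclusions 6-8 or the renal or hepatic parts of 9, control selection can raise the control event total and move losartan towards acceptance under the ±20% rule. Neither the matching nor the consent-based event window, as written, removes this.

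The size cannot be known from the documents. Under the overdispersed event-count assumptions of Step 4, the rise in acceptance runs from about 1 percentage point (L = 4, f = 5%) to about 29 (L = 1, f = 20%). The model gives severity matching no weight and treats all ineligible controls alike. The shift is zero if f = 0, if k = 0 or, at patient level, if q = p.

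This should be fixed, with medium confidence about its practical size. It bears on the primary hypothesis, and the selection component can be removed by design.

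**What to change.** For the primary safety comparison:

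1. Do not relax exclusions 2 and 5-9 for retrospective controls. Match up to two per participant and accept a lower ratio. The overlap argument does not require the same for exclusions with no shown link to adverse events.
2. Give each retrospective control a defined time zero, for example the same elapsed time since first meeting the inclusion criteria as the matched participant had at Day 0, while alive and in hospital.
3. In both groups, count only events that are new or at least one Table 1 grade worse than at time zero, over the same window (for example to discharge or day 14, whichever comes first).
4. Name the severity score used for matching; SOFA, SAPS II and NEWS are already collected. State whether consenting decliners are pooled.
5. Use controls admitted under the clause only in a labelled sensitivity analysis, reporting how many there are and which criterion each carries.

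The cost is an amendment paragraph, a stricter record query and a baseline Table 1 grade for each patient. The downside is fewer controls: the standard error rises about 4% with 80, 15% with 50 and 33% with 30. The size of the eligible pool is not given, so the actual loss cannot be stated.

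### Retrospective controls may carry exclusions 6-9 and have no AE start date, so conditions present at entry can be counted as control AEs; this pulls the safety comparison towards losartan by an unknown amount

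*Combined protocol and SAP*

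**What the plan says.** Safety is the primary hypothesis. Under Sample size and Statistics, "we would accept considering losartan equivalent or superior to the comparison group not receiving losartan (historical or no consent" if total AE/SAEs differ by no more than ±20%. The section does not say whether the 20% is absolute or relative. Historical controls are matched 2:1 on age, sex and disease severity.

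On who may be a control, the Control section opens with an intention: "We will attempt to include controls that meet all criteria for enrollment into the study". It then allows a fallback: "to achieve a ratio of controls to study participants of 2:1 may need include some with exclusion criteria". Prior ACE inhibitor or ARB use is the only exclusion kept. For the treated group, the Losartan section is firm: "Subjects with hyperkalemia, renal dysfunction, or who are taking potassium supplements will not be enrolled into the study".

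On what counts, Definition of an Adverse Event takes in the "safety monitoring data listed on table 1 as well as stoppage criteria for losartan" and requires no causal link. On when counting starts: "AEs will be collected for both study groups, treatment and control from the time the ICF is signed until the subject completes study participation".

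Patients who decline losartan but allow follow-up do have that date: "Patients that agree, will sign the consent form, but will not provide a blood sample for research". Retrospective controls do not: "Controls identified retrospectively will not undergo informed consent as this represents minimal risk". No Day 0, index date or baseline is defined for them.

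**The concern.** The treated group is screened at entry for low blood pressure, vasopressor need, high potassium, poor renal function and markedly raised liver tests. A control admitted under the fallback need not be. Those same conditions, or near versions of them, are on the list of countable AEs. Without a start date for retrospective controls, nothing in the plan separates a condition that was already there from one that arose during follow-up.

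Every such condition that is counted adds to the control total and makes losartan look safer. Hypotension and renal dysfunction are among the serious risks that the protocol itself lists for losartan, so the events most open to this miscounting are the ones that the comparison most needs to measure cleanly.

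**Working it through.** **Step 1. Exclusions set against countable AEs.**

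| Exclusion | Countable as an AE through | Match |
|---|---|---|
| 6: BP below 90 systolic or 60 diastolic, two readings | Stoppage criterion, same limits and repeat rule | Close; worded as developing |
| 7: any vasopressor except norepinephrine ≤0.1 µg/kg/min | Stoppage at norepinephrine >0.1; Table 1 ICU hypotension, Grades 1-2 | Partial; the stoppage rule names norepinephrine only |
| 8: potassium >5.5 mM | Stoppage at >5.5 on at least 2 readings; Table 1 Grade 2 from >5.5 | Close; absolute limit, no baseline |
| 9, renal: Cockcroft-Gault <30 or urine <20 mL/h | Stoppage criterion, same limits | Close; worded as worsening |
| 9, hepatic: LFTs >5 x ULN | Table 1 Grade 3 for AST, ALT and alkaline phosphatase | Close; absolute limit, no baseline |

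**Step 2. Inputs.** From the documents: 50 treated, a 2:1 ratio, hence 2 × 50 = 100 controls, and a 20% margin on an unstated scale. The plan gives no AE rate, alpha or power, so there is no figure of its own to reproduce. Assumed:
- p, the true share of control patients with any AE: 30, 50 or 70%.
- A true losartan excess of 25 points.
- f, the share of all controls with a condition at entry that is counted as an AE: 0, 10 or 20%, taken as independent of later AEs.

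**Step 3. Share of patients with any AE.** The observed control share is p + f(1 − p). At p = 30% and f = 10% this is 0.30 + 0.10 × 0.70 = 0.37. Against 0.55 on losartan, the apparent difference is 18 points instead of 25, and the apparent ratio is 0.55/0.37 = 1.49 instead of 1.83. At f = 10% the shift is 7, 5 and 3 points for p = 30, 50 and 70%.

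Chance of acceptance, from exact binomial sums over 50 and 100 patients. The 20-point rule is observed difference ≤0.20; the ratio rule is observed ratio ≤1.20.

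| p | 20-point rule, f = 0 / 10 / 20% | Ratio rule, f = 0 / 10 / 20% |
|---|---|---|
| 30% | 30 / 61 / 87% | 2 / 13 / 41% |
| 50% | 28 / 52 / 76% | 4 / 15 / 37% |
| 70% | 21 / 39 / 61% | 4 / 12 / 27% |

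At f = 2% the 20-point figures are 36, 33 and 24%.

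**Step 4. Total events instead.** With m events per control and k counted at entry in each affected control, the control total rises by f × k/m, and a true ratio of 1.20 × (1 + f × k/m) reads as 1.20. For m = 3 or 5 and k = 1 or 2:
- f = 10%: a rise of 2.0% (0.10 × 1/5) to 6.7% (0.10 × 2/3); a true ratio of 1.22 to 1.28 reads as 1.20.
- f = 20%: a rise of 4.0 to 13.3%; a true ratio of 1.25 to 1.36 reads as 1.20.

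**Step 5. The offset.** If charts miss a share 1 − p/(p + f(1 − p)) of control patients with an AE, the shift in Step 3 cancels. At f = 10% that share is 19, 9 and 4% for p = 30, 50 and 70%.

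**The case against.** Several points on the other side have weight.

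- **The waiver is a last resort and is broader than this problem.** It also covers exclusions such as chronic interacting medication, other disease and enrolment in another trial. Only the part of its use that falls on exclusions 6-9, and is then counted, feeds f. This stands: f may be small or zero.
- **The wording leans towards new onset.** An AE must arise on study, and the hypotension and renal criteria speak of development and worsening. This stands as intent. It cannot be applied to someone with no start date, and the potassium and liver limits carry no onset wording.
- **Matching on severity may help, and several severity scores are collected.** It may narrow the imbalance. The matching measure is not named, and matching does not stop a condition already present from being counted.
- **Part of the acceptance risk has another source.** The 21-30% at f = 0 under the 20-point rule comes from judging a point estimate with 50 treated patients.

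A reader might infer that the comparison as a whole must favour losartan. The documents do not support that: controls read from charts may have AEs missed, and Step 5 shows that modest under-recording would cancel the effect. A reader might also infer that treated patients are less protected. They are not. The stoppage rules, the 24-hour review of drug-attributable serious events and the DSMB meetings after 5 and 25 patients do not depend on these controls. Only the comparison with controls is exposed.

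**Conclusion.** The gap is real, and it comes from a stated rule combined with a missing start date. If retrospective controls are taken despite exclusions 6-9, this mechanism acts in one direction: it raises the control count and favours losartan. Its size cannot be derived from the documents. Under the assumptions above, f = 10% raises the chance of accepting a true 25-point excess by 18 to 31 points in absolute terms under the 20-point rule (21 to 39% at p = 70%; 30 to 61% at p = 30%) and by about 8 to 11 points under the ratio rule. On an event count it moves the control total by 2.0-6.7%. It is zero if the waiver is not used on these exclusions, and the net direction after chart under-recording is not established. The change should be made because two opposing biases of unknown size are no safeguard, and this one can be removed cheaply.

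**What to change.** 1. Do not take a retrospective control who meets exclusion 6, 7 or 8, or the renal or hepatic part of 9, at the index date. If 100 cannot be found, accept a ratio below 2:1.
2. Give each retrospective control an index date at the same elapsed time since first meeting all inclusion criteria as its matched treated patient's Day 0 (at most 48 hours, by exclusion 13). The control must be alive and in hospital then, and the exclusions are checked at that point.
3. In both groups, count in the safety comparison only AEs that start or worsen in grade after Day 0 or the index date. For participants entering under inclusion criterion 5, set Day 0 at the first standard-of-care losartan dose, so that no AE on losartan is dropped. The AE definition and Table 1 stay as they are.

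The cost is a protocol amendment, a stricter record query, and chart review back to the first standard-of-care dose for inclusion 5 participants. For other treated patients, AEs between consent and Day 0 are still reported but leave the comparison. Treatment and stoppage rules do not change.

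The precision lost is small. With half-width = 1.96 × √[p(1 − p)(1/50 + 1/n)] and matching ignored:

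| p | n = 100 (2:1) | n = 75 (1.5:1) | n = 50 (1:1) |
|---|---|---|---|
| 30% or 70% | 15.6 points | 16.4 | 18.0 |
| 50% | 17.0 points | 17.9 | 19.6 |
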